For the analysis of systemic glucocorticoid dose tapering, conversion to prednisone-equivalent dose may be required, if different glucocorticoids have been administered. Furthermore, the glucocorticoid dose will be expressed as prednisone-equivalent mg/kg body weight/day.

AD-ST-33.04 Effective date: 30-Jun-2017

Version 2.0 | Date 29-Oct-2020 | AD-PR-109.01 Effective date: 26-Jun-2017

Page 21 of 51

Steps to calculate the prednisone equivalent dose (mg/kg/day):

- 1) Select systemic glucocorticoids where route is IV or oral from the 'Systemic glucocorticoids from SD-3 until SD15' form. Reported doses in the 'Systemic glucocorticoids from SD-3 unit SD15' form are daily doses and the number of doses per day is set to 1.
- 2) Select concomitant medications with ATC code H02B (Glucocorticoids) from the 'Concomitant medication' form with IV or oral route of administration. Calculate the frequency per day as follows (this list should not be seen as exhaustive):

Frequency	Description	Number of doses per day
OB, QD	Once a day	1
BID	Twice a day	2
TIB	Three times a day	3
QID	Four times a day	4
QW	Every week	1/7
2xW	Twice per week	2/7
3xW	Three times per week	3/7
NxW	N times per week	N/7
EVERY 2 WEEKS	Every 2 weeks	1/14
QM	Every month	1/30.4375
QAD	Every other day	0.5
Once	Single intake	1/(stop date – start date +1)
PRN	As needed	0
Other	Other	0
UNK	Unknown	0

AD-ST-33.04 Effective date: 30-Jun-2017

Version 2.0 | Date 29-Oct-2020 | AD-PR-109.01 Effective date: 26-Jun-2017

CI	Continuous infusion	0

Note: Administration of glucocorticoids with 'as needed', 'other', or 'unknown' frequency will not be included in the calculation of the equivalent dose.

- 3) If the dose unit is not mg, then the following conversion will be done: 1 g = 1000 mg, 1 mcg = 0.001 mg. IV and oral routes of administration are equivalent.
- 4) Select the weight in kg from the physical examination visit closest to the glucocorticoids administration date.
- 5) Calculate the equivalent dose of prednisone using the following formula:

Equivalent dose (mg/kg/day)= 
$$\frac{Conversion \ Factor * Dose(mg) * Number \ of \ doses \ per \ day}{Weight \ (kg)}$$

where the conversion factor is:

- 1 for prednisone
- 1.25 for methylprednisolone
- 1 for prednisolone
  - Glucocorticoids tapering = glucocorticoids permanently tapered
    - to the same (or lower) dose being administered before the occurrence of MAS (in patients already on treatment for sJIA/AOSD

or

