• by at least 50% of the equivalent dose of prednisone administered at emapalumab treatment start (in those patients who present with MAS at sJIA/AOSD onset).

The daily equivalent dose of prednisone will be compared with the daily equivalent dose of prednisone at SD0.

AD-ST-33.04 Effective date: 30-Jun-2017

Version 2.0 | Date 29-Oct-2020 | AD-PR-109.01 Effective date: 26-Jun-2017

Page 23 of 51

If it is not possible to establish if a patient has been treated for sJIA/AOSD or not before study start for all patients, or if it is not possible to retrieve glucocorticoids dose administered before the occurrence of MAS for all patients who already are treated for sJIA/AOSD, the glucocorticoids tapering endpoint will be changed. In this case the endpoint will be: "glucocorticoids permanently tapered at any time during the study by at least 50% of the equivalent dose of prednisone administered at emapalumab treatment start (SD0).

If glucocorticoid dosing data are unavailable at a given time point, the assumption that dose has not been further tapered from the previous available observation will be made. Glucocorticoid doses will be calculated as (prednisone-equivalent) mg/kg/day.

- MAS remission = resolution of clinical signs and symptoms according to the Investigator (MAS clinical signs and symptoms score ≤ 1) AND normalization of laboratory parameter relevant to MAS as follows:
  - White blood cell count (WBC) and platelet count above the lower limit of normal (LLN)
  - Lactate dehydrogenase (LDH) below 1.5 upper limit of normal (ULN)
  - Alanine aminotransferase/aspartate aminotransferase (ALT/AST) below 1.5 ULN
  - Fibrogen higher than 100 mg/dL
  - Ferritin level decreased by at least 80% from values at screening or baseline (whichever is higher) or below 2000 ng/mL, whichever is lower

If one or more laboratory data are unavailable within the visit window, the LOCF approach will be used.

- MAS remission by week 8 = patients who meet MAS remission conditions in the period SD56  $\pm$  5 days regardless the time of first MAS remission or its duration.
- Survival:

Time to death = date of death - date of first emapalumab infusion + 1

Patients who survive to the end of the study will be censored at the date of last contact. In case in which a patient withdrew consent the censoring date will be the date of withdrawal of consent.

• Time to MAS remission:

AD-ST-33.04 Effective date: 30-Jun-2017

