Version 2.0 | Date 29-Oct-2020 | AD-PR-109.01 Effective date: 26-Jun-2017

Page 24 of 51

date of first MAS remission – date of first emapalumab infusion + 1

Time to the first MAS remission will be calculated from the date of first emapalumab infusion until the date of first MAS remission. Patients who do not meet the criteria of MAS remission will be censored at the date of last contact.

The MAS remission evaluation is based on a combination of assessments, including Investigator assessment and laboratory findings. The latest date of assessments, within the visit window of  $\pm$  3 days around the planned day of the visit, will be used for the calculation of the time to MAS remission.

• Time to achievement of permanent glucocorticoids tapering:

date of glucocorticoids tapering – date of first emapalumab infusion + 1

Time to achievement of glucocorticoids tapering will be calculated from the date of first emapalumab infusion until the date in which the target level of glucocorticoid dose reduction is permanently achieved. Patients who do not meet the criteria of glucocorticoids tapering will be censored at the date of last contact.

• The total daily dose of anakinra, canakinumab, ciclosporin, etoposide, methotrexate, and tocilizumab will be calculated for each subject using the same unit of measurement provided in the concomitant medication log.

Total daily dose = dose \* Number of doses per day

Where the number of doses per day are derived using the same approach for the calculation of the equivalent dose of prednisone equivalent.

• Glucocorticoids tapering to  $\leq 1$  mg/kg/day of the equivalent dose of prednisone:

Achievement of permanent glucocorticoids tapering and last equivalent dose of prednisone is  $\leq 1$  mg/kg/day.

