 AD-PR-109.02
 Effective date: 17-Aug-2020
 Page 9 of 18

	T	<del>-</del>
Section 6.1.7 – Derived variables/ Definition of Biologics	No specification of biologics concomitant used is specified in the SAP version 2.0.	Concomitant use of relevant biologics will be also summarized per section 9.6 however no specification was provided under section 6.1.7.  /  Specifications added: "Relevant concomitant biologics medications will be defined as medications from ATC 4 levels L04AB, L04AC."
Section 6.1.8 - Data Adjustments/Han dling/Convention s/ Handling partial or missing start/stop dates for equivalent daily dose of prednisone, and daily total doses of anakinra, canakinumab, ciclosporin, etoposide, methotrexate, and tocilizumab	No details regarding how to handle partial or missing start/stop dates for equivalent daily dose of prednisone, and daily total doses of anakinra, canakinumab, ciclosporin, etoposide, methotrexate, and tocilizumab	To add detail on how to handle partial or missing start/stop dates for equivalent daily dose of prednisone, and daily total doses of anakinra, canakinumab, ciclosporin, etoposide, methotrexate, and tocilizumab.  /  Imputation of partial/missing medication start or stop dates for equivalent daily dose of prednisone and daily total doses of anakinra, canakinumab, ciclosporin, etoposide, methotrexate, and tocilizumab: -Partial medication end date  • If only month and year are available, medication end date will be imputed to the last day of the corresponding month  • If only year is available, medication end date will be imputed to the 31st of December of the corresponding year -Partial medication start date  • If only month and year are available, medication start date  • If only month and year are available, medication start date

[figure not shown]
Version 2.0 | Date 22-Jul-2021 | AD-PR-109.02 Effective date: 17-Aug-2020 Page 10 of 18

date will be imputed to the
1st day of the
corresponding month
• If only year is available,
medication start date will
be imputed to the 1st of
January of the
corresponding year.
-Medication start and end dates are
both missing, then the record of the
medication will not be considered
(i.e. no derivation of equivalent
dose of prednisone or daily dose of
anakinra,).
-Medication end date is missing
(and medication start date not
missing)
• When medication end date
is missing and "Ongoing" is not ticked
If medication start
date < Study day -
180, then this
record will not be
considered (i.e. no

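### A Concomitant Medication log steroid coded Continuous infusion computes to 0 mg/kg/day, so an unchanged dose can be scored as permanently tapered from SD16

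*SAP*

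**What the plan says.** SAP 6.1.7 takes systemic steroid doses from two CRF modules. One is a dedicated form for SD-3 to SD15, whose doses "are daily doses and the number of doses per day is set to 1". The other is the Concomitant Medication log, which is the only source after SD15. Log records are converted with a frequency table. Its last row, "Continuous infusion", carries 0 doses per day, as do the as-needed, other and unknown rows. Step 5 multiplies conversion factor, dose and doses per day, and divides by weight. The note under the table reads "Administration of glucocorticoids with 'as needed', 'other', or 'unknown' frequency will not be included in the calculation of the equivalent dose". The errata changes the ATC code, the weight rule, the dexamethasone factor and the handling of dates. It leaves the frequency table and the note alone.

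Tapering must be permanent. It is judged either against the pre-MAS dose or as a fall of at least 50% from the SD0 dose. Its time is "date of glucocorticoids tapering – date of first emapalumab infusion + 1". The further endpoint is defined as "Achievement of permanent glucocorticoids tapering and last equivalent dose of prednisone is" at most 1 mg/kg/day. There is one safeguard: "If glucocorticoid dosing data are unavailable at a given time point, the assumption that dose has not been further tapered" is then made from the previous available observation. The word unavailable is not defined.

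Errata 6.1.8 covers missing stop dates:
- **Ongoing ticked:** the record runs to end of study.
- **Ongoing not ticked, start on or after SD0:** the record also runs to end of study.
- **Ongoing not ticked, start from SD-180 to SD-1:** the end date is set to the start date.
- **Ongoing not ticked, start before SD-180:** the record is dropped.

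**The concern.** A table entry of 0 doses per day is harmless if the record is then left out and the day is treated as having no usable dose. It is harmful if the record stays in, because an administered steroid then becomes an observed dose of zero. Continuous infusion falls in the second group: it has the zero factor but is not in the exclusion note. Because the daily-dose form ends at SD15, the effect appears from SD16 as an abrupt fall to zero. A zero satisfies either limb of the tapering definition and the 1 mg/kg/day criterion, so for days after SD15 the error favours the drug.

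The derived dose feeds the tapering proportion with its exact interval, the 1 mg/kg/day count and the Kaplan-Meier analysis (SAP 8.1). Two narrower gaps sit beside it. The SAP does not confirm that a day with only excluded records is unavailable rather than zero. The stop-date rule can also leave days after SD15 without any steroid record.

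**Working it through.** The documents give no figure to reproduce, so the check applies the stated rules to worked cases.

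**Inputs.** From SAP 6.1.7: the step 5 formula, the factor 1.25 for methylprednisolone, 1 dose per day on the SD-3 to SD15 form, 0 for continuous infusion in the log, the 50% threshold against SD0, and time = study day + 1. From SAP 3.2: about 12 patients. Assumed for illustration: methylprednisolone 48 mg/day, weight 30 kg, dose unchanged to SD56, last contact at SD56.

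**Derived dose.**
- SD0 to SD15, from the form: 1.25 × 48 × 1 / 30 = 2.0 mg/kg/day.
- From SD16, log record coded continuous infusion: 1.25 × 48 × 0 / 30 = 0 mg/kg/day, a 100% reduction.
- From SD16, if the day is treated as unavailable: 2.0 mg/kg/day carried forward, a 0% reduction.

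**Endpoint, day by day from SD0 to SD56.**

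| Case (true dose 2 mg/kg/day while the record is unusable) | Record counted as 0 | Day counted as unavailable |
|---|---|---|
| A. Continuous infusion is the only record after SD15 | Tapered at 16 + 1 = 17 days; last dose 0; meets ≤1 mg/kg/day | Not tapered; censored at 56 + 1 = 57; last dose 2 |
| B. Continuous infusion SD16 to SD30, then a valid 2 (or 1.2) mg/kg/day | Not tapered; censored at 57 | Not tapered; censored at 57 |
| C. Continuous infusion SD16 to SD30, then a valid 1 mg/kg/day from SD31 | Tapered at 17 days | Tapered at 31 + 1 = 32 days |

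Case A is a false event. In case B the permanence requirement cancels the error. In case C a true taper is dated 32 − 17 = 15 days early.

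**Missing stop date (errata 6.1.8).** A steroid started on SD-5 with Ongoing not ticked ends on SD-5, so SD16 to SD56 are uncovered. With Ongoing ticked it ends on SD56 and those days are covered. A start on SD-200, not ticked, is dropped. A start on SD0 or later, not ticked, runs to SD56. Ticking Ongoing does not help a continuous-infusion record, because its factor is still 0.

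**Size.** One patient of 12 is 1/12 = 8.3 percentage points. With the exact Clopper-Pearson interval (lower limit the 0.025 quantile of Beta(x, n − x + 1), upper limit the 0.975 quantile of Beta(x + 1, n − x)), an assumed 6/12 = 50.0% (95% CI 21.1 to 78.9) becomes 7/12 = 58.3% (27.7 to 84.8).

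**The case against.** The strongest reply is that the case is remote. The same frequency approach serves six other drugs (SAP 6.1.7, total daily dose), so the continuous-infusion row does not show that steroids were expected by that route. Protocol 4.1.1 describes the high intravenous dose as divided in two. Steroid use is recorded at every follow-up visit (Protocol Table 2), blank CRF fields are not allowed (Protocol 15.1), and a fall to zero at SD16 would show in the patient profile (SAP 12.1). All of this stands as to likelihood. None of it changes the computed value.

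A reader might infer that every zero-factor record is scored as no steroid. The documents do not support that. As-needed, other and unknown records are excluded by the note and so yield no computed dose; the natural reading is that the no-further-taper rule then applies. Only a clarification is needed there.

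A reader might also infer that any pre-SD0 steroid without a stop date produces a false taper. The errata prevents this when Ongoing is ticked. When it is not ticked, the drug may really have stopped: a patient on 2 mg/kg/day to SD15 who then stops is a true taper at 17 days, and carrying the dose forward would wrongly censor that patient at 57. This objection is sound, and it limits what the remedy should do.

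Finally, both modules can hold records for SD-3 to SD15 and no precedence is stated. The SAP does not say that they are added, so a double-counted baseline cannot be read from it.

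**Conclusion.** The point holds for continuous infusion as a matter of arithmetic: the stated rules turn an infused steroid into 0 mg/kg/day. A false permanent taper at 17 days follows only if no other usable record covers the days after SD15; a later valid record above the threshold removes it. For other, unknown and as-needed records the SAP needs to confirm its natural reading. For missing stop dates the gap exists only for starts before SD0 with Ongoing not ticked.

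The documents do not show how many records are affected, and the number may be zero, so there is no basis for saying that the reported tapering rate is in fact wrong. Each affected patient would move it by 8.3 points at n = 12. SAP 4.1 makes all variables exploratory, so the consequence is confined to the description of the tapering endpoints. This is a minor point, but cheap to remove.

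**What to change.** 1. For a continuous infusion, use the recorded daily amount where there is one. Otherwise add continuous infusion to the exclusion note.
2. State that a day after SD15 is unavailable under the existing no-further-taper rule if its only steroid records are continuous infusion without a daily amount, other, unknown or as-needed. The last available dose is then carried forward. Any valid record takes precedence, and a day with no steroid record stays 0.
3. Query pre-SD0 steroids with a missing stop date and Ongoing not ticked before database lock. If a record stays unresolved, keep the errata rule in the main analysis and report a sensitivity count with those patients as not tapered.

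The cost is errata wording, reprogramming of one derived variable, a few data queries and one extra count; no new assessments are needed. The reported tapering rate may be slightly lower, and some true tapers with incomplete records may be missed.

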## 6 PATIENT BACKGROUND TREATMENT AND CARE

### 6.1 GLUCOCORTICOIDS

For a patient to be eligible for the study, an inadequate response to high dose i.v. glucocorticoids administered for at least 3 days as per local standard of care (including but not limited to pulses of 30 mg/kg PDN on 3 consecutive days) must be documented. Inclusion can however occur within less

than 3 days from starting high dose i.v. glucocorticoids, in case the patient's condition and/or lab parameters are rapidly worsening.

High dose i.v. glucocorticoids should not be lower than 2 mg/kg/day of PDN equivalent in 2 divided doses (or at least 60 mg/day in patients of 30 kg or more).

During the study, emapalumab will be initially administered on a background of at least 2 mg/kg/day of PDN equivalent ( or at least 60 mg/day in patients of 30 kg or more).

Glucocorticoid tapering may be initiated as soon as the patient's conditions allow, according to the Investigator's assessment. The tapering scheme can be selected by the Investigator, with the objective of reaching the same (or lower) dose being administered before the occurrence of MAS (in patients already on treatment for sJIA/AOSD) or decreasing by 50% (or more) the glucocorticoid dose administered at initiation of emapalumab treatment (in patients presenting with MAS as first manifestation of sJIA/AOSD).

In the event of disease worsening after glucocorticoid tapering, a higher dose can be re-introduced and maintained until a satisfactory response is achieved according to the Investigator.

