## 7.4 EFFICACY ENDPOINTS

The efficacy of emapalumab in this patient population will be evaluated based on the evolution of the MAS distinct features of cytopenias, liver function and coagulopathy.

In particular the following variables will be assessed:

- Number of patients achieving MAS remission by Week 8 after initiation of emapalumab treatment.
- Time to MAS remission.
- Number of patients for whom at any time during the study glucocorticoids can be tapered *i)* to the same (or lower) dose being administered before the occurrence of MAS (in those patients who are already treated for sJIA/AOSD) or *ii)* by 50% (or less) of the dose administered at emapalumab treatment start (in those patients who present with MAS at sJIA/AOSD onset).
- Time to achievement of glucocorticoids tapering (as defined above).
- Survival time.
- Number of patients withdrawn from the study due to lack of efficacy.

MAS remission is defined as

- ✓ Resolution of clinical signs and symptoms according to the Investigator and
- ✓ Normalization of laboratory parameters relevant to MAS, as follows:
  - WBC and platelet count above LLN
  - LDH below 1.5 ULN
  - ALT/AST below 1.5 ULN
  - fibrinogen higher than 100 mg/dL
  - ferritin levels decreased by at least 80% from values at screening or baseline (whichever is higher) or below 2000 ng/ml, whichever is lower.

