## 6.1.5. Analysis Visit Windows

Statistical analyses will be based on scheduled visits as collected in the case report form (CRF) realigned on study days, which are defined based on the date of first emapalumab infusion (SD0) as follows:

Study Day = date of interest - date of first emapalumab infusion.

The following rules will be applied for MAS remission and glucocorticoid tapering.

- For the assessment of MAS remission and glucocorticoid tapering at Week 8, the SD56±5 days analysis period will be considered. Where several such observations occur in this time window, the one closest to SD56 will be selected. If there are 2 such observations that are equidistant from SD56, the observation that is after SD56 will be selected.
- For the assessment of time to MAS remission, see Section 6.1.7.

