## 8. Efficacy Analysis

## 8.1. Efficacy Analysis

The following binary efficacy endpoints will be described using counts, proportions, and exact Clopper-Person 95% CI:

- Patients achieving MAS remission by Week 8 after initiation of emapalumab treatment
- Patients for whom at any time during the study glucocorticoids can be tapered
- Patients who tapered steroids to ≤1 mg/kg/day of prednisone equivalent dose
- Patients withdrawn from the study due to lack of efficacy

The following time-to-event efficacy endpoints will be analyzed descriptively:

- Time to first MAS remission
- Time to achievement of permanent glucocorticoids tapering
- Survival time

Summaries will include for each observed time, the survival estimate, failure rate, number of events and the number of patients remaining, also called population at risk. The median, lower quartile and upper quartile estimates of time-to-event and their 95% CI will be tabulated in a separate table. A Kaplan–Meier graph will be presented for each time-to-event endpoint.

The efficacy analysis will be based on the All Treated Population. Efficacy analyses will be repeated for the EVAL Population.

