## 11. Changes from Planned Analysis

The Safety analysis set coincides with the All Treated Population and it is not listed in the analysis populations section. The EVAL Population has been added to check the robustness of the efficacy results. The Per-Protocol analysis set has been removed due to the small sample size and the introduction of the EVAL population.

Infusion-related reaction has been added in the safety endpoints (Section 2.2.1).

AD-ST-33.04 Effective date: 30-Jun-2017

Version 2.0 | Date 29-Oct-2020 | AD-PR-109.01 Effective date: 26-Jun-2017

The glucocorticoids tapering endpoint has been modified when it is not possible to establish whether a patient have been treated for sJIA/AOSD or not before study start for all patients or when it is not possible to retrieve glucocorticoids dose administered before the occurrence of MAS for all patients who already are treated for sJIA/AOSD. In this case the endpoint is "Number of patients for whom, at any time during the study, glucocorticoids can be tapered by 50% (or more) of the dose administered at emapalumab treatment start.

IL-10, sCD163, TNFa and IL-18 may be analysed and/or reported separately.

The following have been added:

- safety patient profile reports (Section 12.1)
- descriptive summaries of neutralizing antibody in case of positive ADA results (Section 9.5.3)
- Number and percentage of patients who tapered steroids to  $\leq 1 \text{mg/kg/day}$  of the equivalent dose of prednisone (Section 6.1.7)

No other changes from the analyses specified in the protocol are planned.

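### The SAP adds an undeclared durability condition to the glucocorticoid-tapering endpoint, gives no period for judging it, and does not apply it consistently across sections

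*SAP*

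**What the plan says.** **Protocol.** Section 7.4 lists the endpoint as "Number of patients for whom at any time during the study glucocorticoids can be tapered". The target is either the dose given before MAS or a 50% reduction from the dose at emapalumab start, depending on whether the patient was already treated for the underlying disease. There is no condition on how long the reduction lasts. Section 6.1 provides that if disease worsens after tapering, "a higher dose can be re-introduced and maintained until a satisfactory response is achieved".

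**SAP, derivation.** Section 6.1.7 has "Glucocorticoids tapering = glucocorticoids permanently tapered". The time-to-event variable runs from first infusion "until the date in which the target level of glucocorticoid dose reduction is permanently achieved". The ≤1 mg/kg/day variable in the same section is also built on permanent tapering. No duration or closing date for permanence is given.

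**SAP, endpoint lists.** Section 2.2.2 repeats the protocol's wording. Section 8.1 lists the binary endpoint as "Patients for whom at any time during the study glucocorticoids can be tapered" and, a few lines later, calls the time-to-event endpoint permanent tapering.

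**SAP, visit windows.** Section 6.1.5: "For the assessment of MAS remission and glucocorticoid tapering at Week 8, the SD56±5 days analysis period will be considered". The observation closest to SD56 is used.

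**SAP, declared changes.** Section 11 describes the fallback endpoint, used when pre-MAS treatment or dose cannot be established, without the word *permanently*. It also adds the ≤1 mg/kg/day endpoint, and then states: "No other changes from the analyses specified in the protocol are planned".

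The SAP errata and the post-hoc analysis plan leave the tapering definition as it is.

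**The concern.** The SAP's derivation is narrower than the protocol's endpoint. A patient who reaches the target and later goes back above it meets the protocol's wording but not SAP 6.1.7. Protocol 6.1 foresees exactly that course, so the difference can arise in practice. SAP 11 does not declare the narrowing, and its closing statement is therefore incorrect.

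There are three further gaps:

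- Without a period for permanence, the derivation is incomplete for patients followed beyond SD56 or withdrawn early.
- Read literally, SAP 8.1 makes a patient who tapers and re-escalates a responder in Table 14.2.1 but a censored observation in Table 14.2.3.1.
- The SD56±5 rule covers tapering, but neither SAP 8.1 nor the table list contains a Week 8 tapering endpoint for it to serve.

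At stake are the reported proportion, its confidence interval and the Kaplan-Meier event dates for two of the six efficacy variables in protocol 7.4. The study is open-label, and SAP 4.2 records that efficacy summaries had already been prepared for health authority meetings. A rule left to be settled at programming would not be settled blind to the data.

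**Working it through.** The documents give no planned tapering rate, and the sample size was not formally calculated (SAP 3.2), so there is no figure to reproduce. The check has two parts.

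**1. Do the rules classify patients differently?**

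The rules were applied to six hypothetical dose paths. Assumptions: the target is 50% or less of the SD0 dose, and *permanent* means at target from some day through the patient's last observation. Paths C and D use the extra weekly visits that protocol 3.4 provides when treatment is prolonged.

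| Path | Any time | Permanent | SD56±5 | Event day: any time / permanent |
|---|---|---|---|---|
| A. Target from SD10, held to SD56 | yes | yes | yes | 10 / 10 |
| B. Target SD10, back up from SD30 to SD56 | yes | no | no | 10 / none |
| C. Prolonged treatment: target SD50, back up SD63–SD70 | yes | no | yes | 50 / none |
| D. Prolonged treatment: target first reached SD64, held to SD70 | yes | yes | no | 64 / 64 |
| E. Target SD10, held, withdrawn SD35 | yes | yes | no observation | 10 / 10 |
| F. Target SD10, up SD25, target again from SD45 to SD56 | yes | yes | yes | 10 / 45 |
| Responders | 6/6 | 4/6 | 3/6 | |

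Each pair of rules disagrees on at least one path that the protocol permits:

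- any time against permanent: B and C;
- any time against the window: B and D;
- permanent against the window: C and D.

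Path F is a success throughout, but its event date moves by 35 days (45 − 10). Path A shows that an early, sustained taper is unaffected. The paths were chosen to show where the rules part, so 6, 4 and 3 are not predictions.

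**2. How far can the reported figure move?**

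The planned size is about 12 patients with at least 10 sJIA patients (SAP 3.2). The interval is exact Clopper-Pearson (SAP 8.1): lower limit = Beta⁻¹(0.025; x, n − x + 1), upper limit = Beta⁻¹(0.975; x + 1, n − x).

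One patient is worth 1/12 = 8.3 points, or 1/10 = 10 points.

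| Responders | n = 12: rate (95% CI) |
|---|---|
| 12 | 100% (73.5–100) |
| 11 | 91.7% (61.5–99.8) |
| 10 | 83.3% (51.6–97.9) |
| 9 | 75.0% (42.8–94.5) |
| 8 | 66.7% (34.9–90.1) |

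For n = 10: 10/10 gives 69.2–100, 9/10 gives 55.5–99.7 and 8/10 gives 44.4–97.5.

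The documents do not say how many patients would re-escalate. Starting from an assumed 10 of 12 who ever reach target, one re-escalation gives 9/12 and two give 8/12, a shift of 2/12 = 16.7 points. This illustration separates the any-time rule from the durable one only. A patient who goes back up and is still up at SD56 fails under both permanence and the window.

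**The case against.** The strongest reply is that the SAP has one operational definition and uses it consistently where it derives variables. In 6.1.7 the main definition, the fallback, the time-to-event date and the ≤1 mg/kg/day variable all require permanence. Sections 2.2.2 and 8.1 only name the endpoint. The fallback in 6.1.7 puts both terms in one clause, so the any-time phrase can be read as saying when a taper may occur and *permanently* as saying that it must last.

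That reading is fair, and it stands for the SAP taken alone. A reader might infer three irreconcilable rules, with the result depending wholly on which sentence the programmer follows. The documents do not support that, because the first two can be read together. But the same reading confirms that the SAP is stricter than protocol 7.4, and it does not fit SAP 11, where the fallback appears without *permanently*.

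On the window, 6.1.5 selects an observation and does not define a responder. The errata describes the Week 8 rule as one for MAS remission only, so the mention of tapering may be residual. For a patient whose last visit is SD56, permanence and the window mostly agree. This stands, and it is a reason to delete the mention or give it a stated purpose.

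A reader might also infer that tapering is a main efficacy result or that an error rate is at risk. SAP 4.1 rules out both: every variable is exploratory and there is no hierarchy. Nor do the documents show that the durable definition was chosen because of results already seen. They show only that such results existed.

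**Conclusion.** The point holds as an undeclared durability condition with no stated period, together with labels that do not match it and a window with no endpoint. SAP 11's statement that nothing else changed is not accurate.

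The size depends on how many patients reach the target and then lose it, which is unknown. If none do and all finish at SD56, the any-time and permanent counts are the same. With 12 patients, each one who does lowers the reported rate by 8.3 points under the durable rule. Two would take an assumed 83.3% to 66.7%. The exact intervals are wide and overlap, but this shift comes from the definition and not from sampling, and it can be removed before analysis. The effect is limited to description: the proportion, its interval and the Kaplan-Meier dates.

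**What to change.** - **One definition** for the count, the event date and the fallback in SAP 2.2.2, 6.1.7, 8.1 and 11: at or below the target dose and not above it again through the patient's last study observation, including follow-up beyond SD56. Stopping at SD56 would miss path C and leave path D unclassified.
- **Withdrawals** for safety or lack of efficacy handled as in protocol 12.3.5: non-responder from withdrawal and censored at withdrawal. SAP 6.1.4 does not repeat that rule, so the definition should cite it.
- **Window:** delete tapering from the SD56±5 rule in SAP 6.1.5, or name it as a separate Week 8 summary with its own row.
- **Declaration:** list the durability condition in SAP 11 as a change from the protocol.
- **Protocol endpoint retained:** report the any-time count with its Clopper-Pearson interval beside the durable one in Table 14.2.1.

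The cost is SAP wording and one table row, from data already collected. The taper rate under the durable definition may be lower than under the protocol's wording.
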